12.7 Analysis of Secondary Endpoints

Secondary objectives include to determine the overall cGVHD rate after HCT, NIH moderate-severe cGVHD rate after HCT, cumulative incidence of non-relapse mortality and relapse, adverse hematologic events and infections, immunosuppression-free survival (IFS) at 1 and 2 years from transplantation, progression-free and overall survival at 1 and 2 years from transplantation, and immunologic correlates of B cell depletion.

For the comparison of GVHD, NRM and relapse, competing risks data analysis will be performed using Gray test²⁶ and Fine and Gray competing risks regression analysis²⁵. For PFS, OS, and IFS, standard survival analysis will be performed. Adverse hematologic events will be compared by cumulative incidence measures. All analysis will be repeated by disease group (myeloid vs. lymphoid).

12.8 Analysis of Correlative Studies

The primary analysis for the correlative studies is concerns male recipients with female donors $(F \rightarrow M)$ and H-Y minor histocompatibility antigens (mHA). The analysis will be exploratory without adjustment for multiple testing. Based on the recent report from the [name] lab27, we hypothesize that patients with multiple anti-H-Y antibodies (defined as >=2 antibodies out of 6) at study entry are more likely to develop corticosteroid-requiring cGVHD at one year after HCT. Assuming 50 patients (from both arms) will undergo F→M HCT, if the one-year corticosteroid-requiring cGVHD rate is 55% and 15% for patients with and without multiple anti-H-Y antibodies, respectively, there will be 84% power to detect this difference. This power calculation is based on Fisher's exact test at the two-sided significance level of 0.1 assuming 18 patients in $F \rightarrow M$ 27 will have multiple anti-H-Y antibodies at the study entry. Using the H-Y protein arrays developed in the [name] lab, we measured IgG antibodies specific for DBY (one of HY mHA proteins) in 13 F→M who received rituximab prophylaxis (DFCI#05-377) and 10 F→M who did not receive rituximab. After 6 months post HCT, no one in the rituximab group developed anti-DBY reactivity whereas 4 out of 10 in the control group developed the anti-DBY reactivity (p=0.02). Extrapolating this result to this randomized phase II trial, if the anti-DBY response rates are 5% and 40% in the obinutuzumab and placebo group, respectively, in F \rightarrow M, there will be 88% power to detect this difference (Table). This power calculation is based on Fisher's exact test at the two-sided significance level of 0.1 assuming 25 patients will undergo F

M HCT in each treatment group.

Table. Power for various levels of responses between obinutuzumab and placebo arm

anti-DBY reactivity	(10%, 35%)	(5%, 35%)	(5%, 40%)
Power	57%	79%	88%

When data are available, we will repeat a similar analysis for multiple antibodies and investigate whether a combination of antibody responses is more discriminatory. We will also investigate whether H-Y antibodies measured prior to the initial administration of treatment are predictive of eventual cGVHD using ROC (receiver operating characteristic) curve analysis and multivariable regression analysis after adjusting for treatment arm. In addition, an appropriate statistical analysis will be applied for routine

immunophenotype data analysis including BAFF and B cell recovery as well as for new or existing autosomal mHA that may be associated with development of cGVHD across all recipient and donor sex combinations.

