9. BIOMARKER, CORRELATIVE, AND SPECIAL STUDIES

Approximately 40-50 subjects enrolled in this clinical trial will be F→M subjects, 50% of who will receive obinutuzumab prophylaxis. Comparing obinutuzumab and placebo recipients, we will examine whether effective prevention of alloreactive B cells development, H-Y antibody development or a reduction in H-Y antibody titers correlate with prevention of clinical cGVHD or subsequent severity of cGVHD. We will determine if H-Y antibodies that predate the initial administration of obinutuzumab are predictive of eventual cGVHD development. This latter observation will inform future studies, which may examine earlier administration of obinutuzumab after HCT. All subjects will undergo routine immunophenotyping to monitor the kinetics of BAFF and B cell recovery after obinutuzumab/placebo administration.

Samples will be collected in conjunction with study visits, and no additional study visits are required to fulfill the correlative study objectives.

Peripheral Blood Samples:

Peripheral blood samples will be collected at 3 months, 3.5 months, 6 months, 9 months, 12 months, 18 months, and 24 months from the time of transplantation.

The volume and frequency will not exceed the recommended blood amounts. (It will not exceed 200 mL/day and a maximum of 275 mL in a four week period).

Processing and Shipping Samples:

This is optional for non-DFHCC centers.

Samples will be processed as follows.

- 1. Blood from the first tube will be used for immune cell subset analysis by flow cytometry.
- 2. The remainder of the tube will be used for DNA extraction.
- 3. If the non-DFHCC centers prefer to process the samples on-site, the 1st tube of would be frozen as whole blood, and the DNA would later be extracted at Dana-Farber.
- 4. The 2nd tube will be centrifuged, and 4 mls of plasma will be frozen in vials of 1 ml each.
- 5. The remaining blood from the 2nd tube and the 3rd tube will be used for Ficoll-Paque density gradient sedimentation, and the isolated mononuclear cells frozen in aliquots of approximately 20 million cells per 1ml-vial in 10% DMSO.
- 6. All samples should be stored in 1.8cc Nunc vials.
- 7. Frozen plasma should be stored at -70° C to -20° C. Cryopreserved mononuclear cells should be stored in vapor phase liquid nitrogen.
- 8. Samples older than 48 hours are too old to bank, except for DNA.

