10. STUDY CALENDAR

	Month											
	Pre- transplant	Screening ²	3^3	3.5	6^3	6.5	93	9.5	12 ³	12.5	1810	2410
Obinutuzumab	1		\otimes		\otimes		\otimes		\otimes			
Placebo			\otimes		\otimes		\otimes		\otimes			
Medical		•	•	•	•		•		•		•	•
History												
Physical		•	•	•	•		•		•		•	•
Examination												
CBC with		•	•	•4	•	•4	•	•4	•	•4	•	•
differential												
Pulmonary Function Test		•							•			•
Pregnancy		•										
Test												
Informed Consent		•										
Chimerism analysis ⁵		•			•		•		•		•	•
Tumor Staging		•										
Immunology ⁶			•	•	•		•		•		•	•
Chronic GVHD Assessment ⁹					•		•		•		•	•
Toxicity			•	•	•		•		•		•	•
Assessment												
Infectious	•											
Disease Testing ⁷												
Patient Survey ⁸					•		•		•		•	•

¹As measured from the time of transplantation.

²Screening can begin 60 days from transplantation

³The administration of Obinutuzumab at month 3, 6, 9 and 12 can be +/- 10 days. Similarly, the required follow-up after the first administration of Obinutuzumab occurs +/-4 days 14 days after the administration of Obinutuzumab.

⁴CBC after obinutuzumab should be 14 +/-4 days from the administration of obinutuzumab. CBCs can be performed at local providers, except after the first infusion.

⁵Chimerism studies are required at screening for only subjects who have undergone non-myeolablative transplantation. Chimerism analysis will be performed by single locus microsatellite DNA probes. Total and T cell chimerism measurements should be performed at all evaluation timepoints for all patients regardless of

conditioning regimen.

⁶Quantitative immunoglobulin measurement; Lymphocyte subset analysis for B cells, T cells; ELISA for minor histocompatibility antigens DBY, DBX under the appropriate clinical conditions (sex-mismatch); Plasma banking, and storage of additional mononuclear cells. See Section 9 for additional details.

⁷Testing done in the pre-transplant setting is sufficient to rule out active Hepatitis A, Hepatitis B, Hepatitis C, and HIV infection.

⁸Patient GVHD will be administered to patients during the Month 6, 9, 12, 18, and 24 appointments. Continue to administer at follow-up visits even if patient has been taken off treatment. Survey is located in Appendix E.

⁹Provider cGVHD survey administered at the month 6, 9, 12, 18, and 24 appointments.

¹⁰There is a +/- 21 day window for month 18 and month 24 appointments.

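### The Section 12.8 arm comparison of anti-DBY response neither defines response against the month-3 pre-dose sample nor adjusts for it, although that sample is already scheduled

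*Combined protocol and SAP*

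**What the plan says.** Section 12.8 describes the correlative analyses as exploratory, without multiplicity adjustment. Three parts matter here.

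- **Arm comparison.** The section takes pilot data from DFCI 05-377, where 0 of 13 rituximab-treated and 4 of 10 untreated F→M recipients developed anti-DBY reactivity after 6 months. It extrapolates to this trial: "if the anti-DBY response rates are 5% and 40% in the obinutuzumab and placebo group, respectively". The stated power is 88%, from Fisher's exact test at two-sided 0.1 with 25 F→M patients per arm. A table adds 57% power for 10% vs 35% and 79% for 5% vs 35%.
- **Antibody at entry.** For a different question, prediction of corticosteroid-requiring cGVHD, the plan is "Assuming 50 patients (from both arms) will undergo" F→M transplantation and "assuming 18 patients in" that group "will have multiple anti-H-Y antibodies at the study entry". Multiple means at least 2 of 6.
- **Use of the pre-dose value.** Section 12.8 uses pre-dose H-Y antibodies only as predictors of cGVHD (two-group comparison, ROC curve, regression adjusted for arm). Section 9 likewise says "We will determine if H-Y antibodies that predate the initial administration of obinutuzumab are predictive of eventual cGVHD development".

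The pre-dose data are planned. Section 9 schedules blood at 3 months, and the month-3 immunology panel in the Section 10 calendar (footnote 6) includes DBY and DBX ELISA for sex-mismatched transplants. Section 12.3 does not stratify randomization by antibody status.

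**The concern.** A patient who already has anti-DBY antibody before dose 1 cannot newly develop it. Section 12.8 does not say how such a patient is classified. If counted as a responder, the patient adds a positive result that says nothing about prevention, and the contrast between arms shrinks. If counted as a non-responder, or left out, the 25 per arm is not the number at risk. If existing antibody is expected to clear, that is a separate drug effect which the response rate does not isolate.

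The section itself expects H-Y antibody at entry in a material share of F→M patients, so the question is not remote. Without a definition, the choice could be made after the data are seen. With about 25 patients per arm, an uneven split of pre-dose positives would also feed into the observed difference.

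**Working it through.** **Inputs from the documents (Section 12.8):** rates of 5% vs 40%; 25 per arm; Fisher's exact test, two-sided 0.1; stated power 88%; 18 of 50 = 36% with at least 2 of 6 anti-H-Y antibodies at entry.

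**Input not in the documents:** b, the share anti-DBY positive before dose 1. It is assumed at 0%, 10%, 20% and 36%. The top value borrows the multiple-antibody figure for illustration only; it is not an anti-DBY rate.

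**1. Reproduce the plan's figure.** The arcsine approximation with continuity correction is z = 2[asin√(p2 − 1/2n) − asin√(p1 + 1/2n)] / √(2/n), with power Φ(z − 1.645). For n = 25, 1/2n = 0.02:

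- 5% vs 40%: z = 2(asin√0.38 − asin√0.07)/√0.08 = 2(0.6642 − 0.2678)/0.2828 = 2.803. Power = Φ(1.158) = 87.7% (stated 88%).
- 5% vs 35%: 78.5% (stated 79%).
- 10% vs 35%: 57.2% (stated 57%).

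Full enumeration of Fisher's test (sum of binomial probabilities over all tables with p ≤ 0.1) gives 90.5%, 82.0% and 59.9%. The stated figures are sound under their own inputs and slightly conservative. The rest uses enumeration.

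**2. Pre-dose positives kept and counted as responders in both arms.** With 5% and 40% as new-onset rates among negatives, the observed rate is b + (1 − b)p, and n stays at 25 per arm.

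| b | obinutuzumab | placebo | exact power |
|---|---|---|---|
| 0% | 5% | 40% | 90% |
| 10% | 0.10 + 0.90×0.05 = 14.5% | 0.10 + 0.90×0.40 = 46% | 71% |
| 20% | 24% | 52% | 57% |
| 36% | 39.2% | 61.6% | 40% |

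**3. Restrict to month-3 negatives.** Then n = 25(1 − b), taken as 22, 20 and 16. The result depends on what 5% and 40% refer to:

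| b | n per arm | 5%/40% hold among negatives | 5%/40% are all-patient rates, rescaled by 25/n |
|---|---|---|---|
| 10% | 22 | 85% | 91% (5.7% vs 45.5%) |
| 20% | 20 | 81% | 92% (6.25% vs 50%) |
| 36% | 16 | 66% | 94% (7.8% vs 62.5%) |

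The last column treats prior positives as non-developers within the all-patient rate, so the rates among negatives are higher. The documents do not say whether the 13 and 10 pilot patients were restricted to antibody-negative patients, so neither column can be ruled out.

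**4. Chance imbalance.** If 18 of 50 were positive at entry and split at random 25/25, the hypergeometric probability that the arms differ by 4 or more positives is 38%. With 10 of 50 it is 29%.

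**The case against.** The strongest reply is that Section 12.8 gives a power assumption, not a full analysis specification, and that its wording points to new onset. Patients in the source data developed reactivity, and Section 2.4 describes the same data as antibodies arising between 6 months and 1 year. This stands in part: the plan does not state that only post-treatment status will be used, and that reading rests on silence. But no definition is given for this trial.

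Several stronger readings are tempting and are not supported:

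- **That 36% of patients will be anti-DBY positive at entry.** The 18 of 50 counts patients with at least 2 of 6 H-Y antibodies, not DBY specifically. Section 2.4 reports that none of the patients with detectable DBY-2-binding B cells at 6 months yet had circulating anti-DBY-2 IgG. That concerns one epitope and a small group, but it is a reason to allow for values near zero, where the 88% stands.
- **That the comparison is biased.** Assignment is randomized, and chance imbalance is covered by the test's type I error. Adjustment buys precision and clarity.
- **That power necessarily falls.** If 5% and 40% are all-patient rates, restricting to negatives loses nothing.
- **That 5% on obinutuzumab is unreachable.** Section 2.4 reports H-Y IgM and IgG becoming undetectable for at least 6 months in 11 rituximab responders, while 4 non-responders stayed IgG positive. Section 9 also names falling titre as of interest, so new antibody is not the only question.

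The analysis is exploratory and touches no primary endpoint, sample size or stopping decision. That limits the severity.

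**Conclusion.** The point holds as a minor, low-cost improvement. The anti-DBY arm comparison lacks a response definition tied to the month-3 pre-dose sample and makes no stated use of that value, although it will be collected and the section expects some H-Y antibody at entry. The 88% is not an error and the comparison is not biased.

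The size depends on an unknown, the pre-dose anti-DBY share, and on what the planning rates mean. Over an assumed 10% to 36%, power runs from 71% down to 40% if pre-dose positives count as responders in both arms and never clear. Among negatives it runs from 85% down to 66% if the planning rates apply to them, and is about 91% to 94% if those rates apply to all patients. With a share near zero nothing changes. The spread between these readings is itself the reason to fix the definition in advance.

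**What to change.** In Section 12.8:

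1. Define anti-DBY response relative to the month-3 pre-dose sample, including how patients already positive are classified and the post-dose time window.
2. Compare the arms in all F→M patients, stratified by or adjusted for month-3 anti-DBY status (exact stratified test or exact logistic regression), or by ANCOVA on log titre with month-3 log titre as covariate.
3. Report new reactivity among month-3 negatives alongside.
4. Present power over an assumed range of pre-dose positivity, stating whether 5% and 40% refer to negatives or to all patients.
5. Apply the same rules to the planned repeat for multiple antibodies.

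The cost is analysis-plan wording and slightly more analysis. No extra visit, sample or patient is needed. The quoted power may become less favourable than 88%.

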2.4 Correlative Studies Background

While many mHA are likely involved in cGVHD, the F→M HCT model provides a convenient set of known mHA whose antibody responses can be tracked. The [name] lab has identified a series of 9 highly immunogenic minor histocompatibility (mHA) proteins on the Y chromosome (H-Y proteins). Subjects who underwent F→M HCT, were found to have significantly higher levels of anti-H-Y IgG antibodies, which correlated with a higher rate of cGVHD after HCT. As shown in Figure 3, H-Y antibodies are associated with a higher probability of cGVHD but lower levels of relapse, displaying both the GVHD and GVL

Figure 3: Association between anti-H-Y antibodies with cGVHD and protection from relapse

effects of the allo-immune response.⁸ While antibody responses in humans are correlated with cGVHD, it is important to note that in the mouse, deposition of IgG is involved in the pathology of cGVHD.

The DBY-2 peptide (KNDPERLDQQLANLDLNSEK) contains the DBY-2 epitope, frequently recognized in allogeneic F→M antibody responses that occur following HCT. [name] was able to demonstrate the presence of circulating B cells expressing immunoglobulin receptors that specifically bind DBY-2. In a retrospective analysis of 28 subjects undergoing F→M HCT without prior cGVHD, DBY-2-binding B cells were detected in 16 subjects (57%) 6 months after HCT, with appropriate negative controls, including healthy female donors or male donor PBMC incubated with high-titer anti-DBY-2 IgG (Figure 4).²⁰ Importantly, 15 of these 16 developed cGVHD, including 6 who were diagnosed at the time of the anti-DBY-2 analysis. The absolute and relative number of DBY-2-specific B cells was significantly higher 6

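### Section 12.8 plans ROC analysis of H-Y antibodies in about 40-50 patients with no optimism correction; if several antibodies are fitted jointly, the apparent AUC averages about 0.69-0.74 even when none predicts cGVHD

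*Combined protocol and SAP*

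**What the plan says.** Section 12.8 (Analysis of Correlative Studies) declares the correlative work exploratory and makes no multiplicity adjustment. It fixes one predictor in advance, "multiple anti-H-Y antibodies (defined as >=2 antibodies out of 6) at study entry", and gives it a power calculation. Three further elements matter here.

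- After the anti-DBY comparison between arms, it says a similar analysis will be repeated for multiple antibodies and that the team will "investigate whether a combination of antibody responses is more discriminatory".
- The next sentence adds that H-Y antibodies measured before treatment will be examined to see whether they "are predictive of eventual cGVHD using ROC (receiver operating characteristic) curve analysis and multivariable regression analysis after adjusting for treatment arm".
- The patients are the F→M recipients. Section 9 expects: "Approximately 40-50 subjects enrolled in this clinical trial will be" of this type. Section 12.8 uses the upper end: "Assuming 50 patients (from both arms) will undergo" such a transplant. Section 9 also makes sample processing and shipping optional outside DF/HCC, so the usable number may be lower.

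The plan does not say how many antibodies enter the regression, whether the ROC curve is drawn for a single rule or for a fitted model, or how a combination would be chosen. It contains no cross-validation, bootstrap, hold-out set, shrinkage or external validation.

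**The concern.** An AUC computed in the patients used to choose or fit the predictor is biased upward. The bias is large when candidate antibodies are many relative to events. The plan names six antibodies in its rule, and Section 2.4 describes "a series of 9 highly immunogenic minor histocompatibility (mHA) proteins on the Y chromosome", against a few dozen patients.

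The exploratory label does not deal with this. It tells the reader that p-values are unadjusted. It does not say that an AUC around 0.7 may be what uninformative antibodies produce.

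A second, conditional issue is treatment arm. If the ROC curve comes from a model that includes arm, part of the discrimination belongs to treatment and not to the antibodies.

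Section 9 says the pre-treatment antibody finding is meant to feed into later trials that might start the drug sooner after transplant. An inflated AUC could therefore influence later design.

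**Working it through.** **1. The plan's own figure.** Inputs from 12.8: "if the one-year corticosteroid-requiring cGVHD rate is 55% and 15% for patients with and without multiple anti-H-Y antibodies", and Fisher's "exact test at the two-sided significance level of 0.1 assuming 18 patients in" the F→M group, which leaves 50 − 18 = 32 without multiple antibodies. Exact enumeration with 0.05 in each tail gives power of 85.0%; a continuity-corrected formula gives 84.6%. The stated 84% is reproduced.

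**2. Event counts.** One-year corticosteroid-requiring cGVHD: 18 × 0.55 + 32 × 0.15 = 9.9 + 4.8 = 14.7 events in 50 (29.4%). The ROC sentence concerns eventual cGVHD, which is more frequent. If the two-year overall cGVHD rates in Section 2.1 (48% with rituximab, 60% in controls) carried over to 25 patients per arm, there would be 25 × 0.48 + 25 × 0.60 = 27 events (54%). Rates of 29.4% and 50% were therefore both simulated.

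**3. Antibody prevalence (assumption).** The plan gives none. For six independent antibodies, solving 1 − (1−p)^6 − 6p(1−p)^5 = 18/50 gives p = 0.206. Prevalence of 0.25, correlated antibodies and continuous antibodies were also tried.

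**4. Apparent AUC with no true association.** Antibodies were generated independently of cGVHD, and the AUC was taken in the same patients (300-2000 runs per setting).

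| Procedure | n = 50 | n = 40 |
|---|---|---|
| Six antibodies, joint logistic fit, 29.4% events | 0.71 (5th-95th percentile 0.61-0.82; ≥0.70 in 53-56% of runs) | 0.74 (0.62-0.86; 68-69%) |
| Same, 50% events | 0.69 | 0.71 |
| Same, 29.4% events, latent correlation 0.5-0.8 | 0.68-0.70 | 0.70-0.72 |

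Over all settings tried, a joint fit gave 0.58-0.63 with two antibodies, 0.62-0.66 with three and 0.74-0.80 with nine. With six candidates, the best single antibody gave 0.57-0.67 and the best unweighted subset 0.60-0.66. The fixed ≥2-of-6 rule stayed at 0.50.

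**5. Scale.** At the rates in step 1, the ≥2-of-6 rule has sensitivity 9.9/14.7 = 0.673 and specificity (32 × 0.85)/(50 − 14.7) = 27.2/35.3 = 0.771. Its AUC would be (0.673 + 0.771)/2 = 0.72. The effect the plan hopes to find thus looks much like a joint fit of six uninformative antibodies.

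**6. Treatment arm.** At the design rates of 38% and 21% (Section 12.2), arm alone gives 0.5 + (0.38/0.59 − 0.62/1.41)/2 = 0.602. Adding six uninformative antibodies raises the simulated apparent AUC from 0.604 to 0.756 (n = 50) and from 0.606 to 0.783 (n = 40). The apparent gain over arm is 0.15-0.18, so the gain needs validating too.

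**7. What correction achieves with no true association.**

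- Bootstrap optimism correction (n = 50, 29.4% events, 200 runs × 100 resamples) lowers the mean from 0.72 to 0.58 with binary antibodies and from 0.71 to 0.57 with continuous ones. Across the checks it leaves about 0.56-0.60.
- Repeated 5-fold cross-validation (600 runs per setting, prevalence 25%) averages about 0.50-0.52 and reaches 0.70 in only 2-6% of runs.

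**The case against.** A reader might infer that 12.8 prescribes one procedure: search for the best antibody combination, then report its ROC curve for cGVHD. The text does not support that. The combination sentence directly follows the anti-DBY comparison of obinutuzumab with placebo, and may well mean responses that separate the arms. The ROC sentence is a separate one about pre-treatment antibodies. It does not say that six antibodies are fitted together or that subsets are searched. An ROC curve for the ≥2-of-6 rule alone would also fit the wording, and that would be unbiased.

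A reader might also take about 15 events as the plan's count for the ROC analysis. That count is for one-year corticosteroid-requiring cGVHD; eventual cGVHD would give more. This stands, but at 50% events the joint-fit AUC falls only to 0.69 (n = 50) or 0.71 (n = 40).

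Nor do the documents say that the AUC will be used to choose an antibody panel. Section 9 says only that the finding will inform later work on earlier dosing.

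Finally, the work is labelled exploratory, the ≥2-of-6 rule already comes first, and validation could be added at analysis without new data. All of this is true and keeps the point small. It does not remove it: multivariable regression of antibodies on cGVHD is planned in a small sample, and nothing tells the analyst or the reader to validate the AUC.

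**Conclusion.** The point holds conditionally. If several antibodies are fitted jointly and the AUC is read from the same 40-50 patients, six uninformative antibodies average about 0.69-0.74. Less flexible searches inflate less: about 0.60-0.66 for the best unweighted subset. The pre-specified ≥2-of-6 rule is not affected.

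The figures rest on assumed prevalence (about 20-25%), largely independent antibodies, 30-50% events and a logistic model. Strong correlation lowers the mean only to 0.68 at n = 50.

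The documents do not support the stronger statement that 12.8 as written will yield an AUC near 0.7 from noise, because they leave the model and the purpose of the combination open. The primary and secondary efficacy analyses are untouched. This is a worthwhile improvement to an exploratory analysis, not a flaw in the trial.

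**What to change.** Add two or three sentences to Section 12.8:

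1. The main ROC result is the AUC, with confidence interval, of the already pre-specified ≥2-of-6 rule.
2. For any combination selected or fitted in these data, report a repeated cross-validated AUC with selection and fitting both redone inside each fold. This is preferred to bootstrap optimism correction, which removes only part of the bias here.
3. If treatment arm is in the model, report the gain in cross-validated AUC over arm alone.

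It would also help to state whether the search for a more discriminatory combination is aimed at separating the arms or at predicting cGVHD.

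The cost is a little more analysis code and text, with no new patients, samples or visits. The drawback is a lower and more variable reported AUC.
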